9.8. Quality control

Outline of data extraction procedures. The study team will request CMS CCW claims data for all beneficiaries who received the RZV vaccine and a random sample of beneficiaries who did not receive the RZV vaccine that will enable a 1:4 ratio of exposed to unexposed. CMS provides research identifiable data that contain dates of service, date of birth, and zip code. However, to preserve anonymity and confidentiality, the data do not contain personal identifying information, such as name, address, Medicare identification number, or social security numbers. A de-identifiable beneficiary ID is used to link data files; however, CMS does not provide the key that links the de-identified beneficiary ID to personal identifying information.

The data extraction procedures to ensure the quality and integrity of the data are:

- **CMS data acquisition-retrospective data collection/analysis**. All claims data acquired will include year's 2017 (baseline pre-period for 2018), 2018, 2019, 2020, and 2021 (follow-up period for 2019) for beneficiaries identified for the study.
- **Extraction of individual data**. All data extracted for individual level analyses will undergo reviewed by a second programmer to ensure accuracy of the programming code. Programming code includes those used to identify exposed and unexposed individuals eligible for the study, to apply the inclusion and exclusion criteria to identify the study cohort and to identify individuals eligible for the planned analyses.

- **Dataset check**. All programs and outputted datasets will undergo a 3-person reviewinitial programmer, second programmer and project coordinator. The initial programmer is responsible for the first review of his/her programs and output. A second programmer, whose sole responsibility is quality control, will be responsible for secondary review of the task list and all programs. The project coordinator who oversees the task order for each programming serves as the third reviewer who will be responsible for review of all output to ensure that it adheres to the protocol.
- **Perform consistency checks**. Files will be inspected for correct application of inclusion criteria as outlined in this document and stored in a manner consistent with DUA specifications. Once the list of inconsistencies is reviewed, discrepancies can either be confirmed or corrected, as applicable. Once completed, the data files will again be re-transferred in a secure manner, in the required format for a final check, database freeze/archival, and lock of the dataset.

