9.2.2. Study population (Amended 15 July 2022)

The study population will be comprised of all US Medicare beneficiaries who received the RZV vaccine (i.e., exposed) in 2018 through 2020 as well as a random sample of Medicare beneficiaries who did not receive the RZV vaccine but who had at least one preventive care visit (*i.e., comparator group*), as defined in Section 9.7.5. The study population is a longitudinal cohort that is followed over time until they are no longer in Medicare. This means there will be continuity of their data over time, i.e., there is not a new random sample selected each study year.

Study inclusion / exclusion criteria

US Medicare beneficiaries who meet the following criteria will be included in the study:

- 1. Age 65 and older at the date of the RZV vaccination or preventive care visit for the RZV unvaccinated comparator, **AND**
- 2. Enrolled in Medicare due to age or ESRD as the original and current qualifying reason, **AND**
- 3. Continuously enrolled in Medicare Parts A, B, and D fee-for-service for at least 365 days preceding the date of RZV vaccination or preventive care visit for the RZV unvaccinated comparator. Continuous *enrollment* is determined by Medicare enrollment in the month of the RZV vaccination or preventative care visit and *enrollment* in at least 11 of the 12 preceding months.

Beneficiaries enrolled due to ESRD or receiving dialysis are included in the study population as this condition is prevalent among US Medicare beneficiaries aged 65 and older, and this is a subgroup in which RZV use may be common. The requirement for continuous enrollment in Medicare Parts A, B, and D in the 365 days, *allowing one calendar month gap*, before the RZV vaccination or preventive care visit will ensure complete data on all services covered by Medicare on a fee-for-service basis in the baseline study period for the cohort design. Parts A and B provide information on the HOI and Part D provides information on RZV exposure.

Beneficiaries who satisfy the following criteria will be excluded:

- 1. Continuously enrolled only in Medicare Part C in the baseline period, OR
- 2. Enrolled in Medicare due to disability as the original qualifying reason for enrollment.

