9.5. Study size

9.5.1. Projected study size

CMS CCW Medicare claims data will be obtained for up to 20 million Medicare beneficiaries. This will include all RZV vaccinees in 2018 through 2020 in addition to a random sample of Medicare beneficiaries who did not receive RZV and had a preventive care visit. The estimated sample size for the SCRI design with vaccinees (Table 4) and the cohort design with vaccinees and the unvaccinated comparators (Table 4) needed to detect the specified relative risk with 80% power is attainable.

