9.7.5. Analysis population (*Amended 15 July 2022*)

Population for the SCRI design analyses

Only the cases of new-onset gout, GBS and SVT recorded in the RZV exposed cohort during either the risk or the control windows will be included in the respective HOI SCRI analysis.

Population for the cohort design analyses

The study population for the cohort design will comprise all RZV exposed and RZV unvaccinated comparators with a preventive care visit who satisfy the inclusion criteria. With the cohort design, to exclude prevalent cases of the HOI prior to the index date, all *participants* who had the HOI at any point in the 365-day pre-vaccination baseline period will be excluded.

Generating an index date for unexposed comparators. In an attempt to control healthy user bias among individuals who receive the RZV vaccine, the unvaccinated comparators will be selected from individuals who have at least one preventive care visit. The steps described below will be performed separately for Dose 1 and Dose 2.

- 1. Create a pool of eligible comparators with at least one preventive care visit.
 - The pool of eligible comparators are unvaccinated individuals who had at least one preventive care visit, which is defined as having at least one visit for a routine adult annual exam OR at least one preventive screening intervention performed (Table 2).
 - To ensure complete data for the baseline period preceding cohort follow-up, individuals must be continuously enrolled in Medicare Parts A, B, and D for a minimum of 365 days preceding the preventive care visit. *Continuous enrollment is determined by Medicare enrollment in the month of the preventative care visit and enrollment in at least 11 of the 12 preceding months.* Visits that do not satisfy this criterion will be excluded. For individuals with multiple preventive care visits, only visits that do not meet the eligibility criterion will be excluded. For individuals with only one preventive care visit, the entire person will be excluded if the visit does not meet eligibility criterion.
- 2. Randomly select one preventive care visit from eligible comparators. For an individual to be eligible as a comparator, the individual must not have had RZV at any time in available history prior to or on the day of the preventive care visit.
- 3. The preventive care visit is the index date for the unexposed comparator.

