Censoring events. Exposed person-time will be defined as the period between the index date and the earliest of the following events:

- End of study period (defined as the lesser of 183 days after the index date or Dec 31. 2021)
- Date of disenrollment from Medicare Parts A, B, and D
- Date of death
- Date of *Shingrix* vaccination among comparators
- Date of *Zostavax* vaccination
- Date of first diagnosis of the outcome of interest.

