The effect estimates generated from the time-dependent Cox proportional hazards model will be a hazard ratio for Dose 1 relative to unexposed and a hazard ratio for Dose 2 relative to unexposed. Both hazards are generated in the same model with the full cohort, using time since the Dose 1 index date or the preventive care visit.

Sensitivity analysis for receipt of the Dose 1 and Dose 2 on schedule. The sensitivity analysis will be restricted to the sub-sample of individuals who receive both RZV doses on schedule per US label. This will test the sensitivity of the primary and secondary analyses, which examine the HOI incidence regardless of the dose spacing. This will follow the primary separate dose analysis and the secondary combined dose analysis.

Supplemental analysis

Some individuals in the analysis may contribute person-time both to the comparison group and (subsequently) to the RZV-vaccinated group. At CBER's request, a supplemental analysis will be conducted for the primary analysis, excluding from the control arm those *participants* who received RZV at any point, so that each *participant* contributes person-time to only one arm.

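### Later RZV recipients enter the comparator pool in full and never-vaccinated people only at an unstated, unweighted sampling fraction, so the PMR, GCA and ION hazard ratios can be biased if the outcome alters later uptake

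*Combined protocol and SAP*

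**What the plan says.** Three sections describe the data request in the same way. Section 9.8 asks for "all beneficiaries who received the RZV vaccine and a random sample of beneficiaries who did not receive the RZV vaccine". Section 9.5.1 adds the calendar window: "This will include all RZV vaccinees in 2018 through 2020 in addition to a random sample of Medicare beneficiaries who did not receive RZV". Section 9.2.2 describes the comparators as "a random sample of Medicare beneficiaries who did not receive the RZV vaccine but who had at least one preventive care visit" and refers to 9.7.5 for the definition.

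Section 9.7.5 judges RZV status only up to the visit: "the individual must not have had RZV at any time in available history prior to or on the day of the preventive care visit". The visit is then drawn at random ("Randomly select one preventive care visit from eligible comparators"). Section 9.7.6 lists Shingrix "vaccination among comparators" as a censoring event, and 9.7.9 states the consequence: "Some individuals in the analysis may contribute person-time both to the comparison group and (subsequently) to the RZV-vaccinated group". Section 9.7.9 also plans a check: "At CBER's request, a supplemental analysis will be conducted for the primary analysis, excluding from the control arm those" who were vaccinated at any time.

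No section gives the sampling fraction, a sampling weight, or a rule that draws later vaccinees at the same rate as never-vaccinated beneficiaries. The limitations in 9.9 do not raise the matter.

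**The concern.** The request sorts people by whether they received RZV at any time in 2018-2020. For someone whose preventive visit precedes vaccination, that is information from after the index date. A comparator who will be vaccinated later is certain to be in the file; one who never will be is there with probability s.

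This matters if having the outcome changes the chance of later vaccination. Under Table 3, PMR and GCA cases have two oral glucocorticoid prescriptions, so a change in uptake after onset is plausible, though the documents give no figure. If cases are vaccinated less often afterwards, later vaccinees carry comparator time with too few events, and over-representing them lowers the comparator rate. Excluding everyone ever vaccinated has the opposite effect: person-time that is selectively event-free is removed and the comparator rate rises.

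The comparator rate is the reference for two of the four primary outcomes and for ION.

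**Working it through.** **1. The plan's own figure.** Table 5 is reproduced by the Poisson-regression formula with exposed share p = 0.2 and the baseline read as a yearly rate over 0.5 year:

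N = [1.960·√(1/(p(1−p))) + 0.8416·√(1/(1−p) + 1/(p·RR))]² / (baseline · 0.5 · (ln RR)²)

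PMR, RR 2: (4.900 + 1.630)² / (0.000405 · 0.5 · 0.4805) = 438,239, as stated. GCA, RR 3, gives 723,361 against 723,362. All nine rows agree within 1. Exposure of a full year gives 219,119 for PMR and does not fit. Table 5 does not depend on the sampling rule; it is used here only to fix the event counts.

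**2. Precision at the planned size** (9.2.2: 2 million exposed, 8 million comparators; full half-year follow-up and no covariate adjustment assumed).

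- PMR: 2,000,000 · 0.000405 · 0.5 = 405 events and 1,620 events; SE = √(1/405 + 1/1620) = 0.056.
- GCA: 92 and 368 events; SE = √(1/92 + 1/368) = 0.117.
- ION: no baseline rate is given.

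**3. How large later uptake can be.** At most all 2 million eligible vaccinees could have been comparators first. If the 8 million are a fraction s of never-vaccinated people, later uptake P ≤ 2/(2 + 8/s). If the 8 million already include the later vaccinees, P ≤ 2/(2 + 6/s). For s = 0.25 the limits are 5.9% and 7.7%; for s = 0.5, 11.1% and 14.3%. The range of s is an assumption.

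**4. Model** (assumptions: constant event hazard h, rare events; constant uptake hazard u = −ln(1−P)/548 per day; uptake multiplied by 1−q after an event; follow-up 183 days, cut at the event or RZV).

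- All person-time: A = (1 − e^(−183u))/u
- Never-vaccinated person-time: B = 183·e^(−548u)
- Events in the never-vaccinated, divided by h: C = e^(−548u(1−q)) · (1 − e^(−183uq))/(uq)
- Sampled comparator rate / h = [(A − C) + sC] / [(A − B) + sB]
- Estimated HR when the true HR is 1 = the reciprocal; with never-vaccinated comparators only, B/C.

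Example, s = 0.25, P = 5.9%, q = 0.5: A = 181.2, B = 172.2, C = 176.6. Rate ratio = (4.5 + 44.2)/(8.9 + 43.1) = 0.936, so HR = 1.068. Never-vaccinated only: 172.2/176.6 = 0.975.

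| s | P | Later vaccinees' share of pool | HR, 50% fall | HR, 80% fall | Never-vaccinated only, 50% fall |
|---|---|---|---|---|---|
| 0.25 | 5.9% | 20% | 1.068 | 1.114 | 0.975 |
| 0.25 | 7.7% | 25% | 1.086 | 1.148 | 0.967 |
| 0.5 | 11.1% | 20% | 1.043 | 1.073 | 0.952 |
| 0.5 | 14.3% | 25% | 1.055 | 1.093 | 0.938 |

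With q = 0 every entry is 1.00. With a 25% rise in uptake (q = −0.25) the primary HR is 0.96 to 0.98. At s = 1 the primary distortion vanishes for any q.

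**5. Against the standard errors.** ln 1.04 = 0.039 and ln 1.09 = 0.086. These are 0.7 and 1.5 SE for PMR, and 0.3 and 0.7 SE for GCA. An HR of 1.15 (ln = 0.140) is 2.5 SE for PMR and 1.2 SE for GCA.

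**6. Does weighting repair it?** Giving never-vaccinated comparators weight 1/s turns the ratio in step 4 into [(A − C) + C]/[(A − B) + B] = A/A = 1. A simulation of 8 million people with s = 0.28 and uptake of 0.10 per year, halved after an event, gave a true rate of 0.0200, an unweighted rate of 0.0179 and a weighted rate of 0.0202. Its uptake exceeds the limits in step 3, so it serves only to check the remedy.

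**The case against.** The best defence is that the comparator rule itself is sound: 9.2.2 refers to 9.7.5, which uses status at the visit. Section 9.8 outlines a data request and does not say that the analysis is unweighted. Comparators are censored at RZV, dual contribution is disclosed, and a supplemental analysis requested by the regulator is planned. Because it errs in the opposite direction, a divergence from the primary result would give a warning.

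Only part of this stands. A visit-based eligibility rule cannot undo a file already drawn on later receipt, and no section supplies the weights. Censoring stops exposed time counting as unexposed but leaves the inclusion probabilities unequal. The covariate and propensity methods in 9.7.10 use baseline variables, so they do not correct selection on a later vaccination. A divergence would also be hard to interpret, since later vaccinees may differ in baseline risk, and neither analysis would give the right value.

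The objection does succeed on size. A reader might pair s = 0.25 with 20 to 30% later uptake and obtain 1.19 to 1.51, but the plan's 2 million and 8 million do not allow that uptake at that s. Nor do the documents support saying that the supplemental analysis would hide a true signal of the targeted size: at 0.94, RR 2 becomes 1.88 and RR 3 becomes 2.82.

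**Conclusion.** The inconsistency is real and amounts to more than missing detail: as written, inclusion in the primary comparator pool depends on vaccination after the index date, and nothing in the plan corrects for it.

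It does not follow that the hazard ratios are biased, which a reader might infer. The bias depends on s and on how the outcome changes later uptake, and the documents give neither. Under the assumptions in the working, a 50% fall produces about 1.04 to 1.09, and an 80% fall at s = 0.25 up to about 1.15. At a 50% fall the distortion alone stays below 2 SE for both PMR and GCA; only the extreme case exceeds 2 SE, and only for PMR. The supplemental analysis, at about 0.94 to 0.975 for a 50% fall, conditions on the future in the other direction and is not a clean check. The model leaves out death before vaccination, covariate adjustment, and differences in baseline risk between later vaccinees and the never-vaccinated.

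**What to change.** Define comparator sampling by RZV status at the preventive visit, and state one of two rules in the SAP:

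- draw later vaccinees into the comparator pool at the same random fraction as never-vaccinated beneficiaries; or
- report s and weight never-vaccinated comparators by 1/s in the Cox models, with robust variance.

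Align 9.2.2, 9.5.1, 9.7.5 and 9.8 with the chosen rule. If those sections already mean status at the visit, say so, and say how comparators are told apart from the full set of vaccinees in the same file. Keep the supplemental analysis requested by CBER, but state that it conditions on future vaccination and name the expected direction of error.

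No new data are needed, since the sponsor should know s from its own request. The cost is somewhat larger standard errors, from the weights or from dropping some later vaccinees. That is affordable: 8 million comparators are planned, against 350,591 required for PMR at RR 2 and 578,689 for GCA at RR 3.

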9.9. Limitations of the research methods

The section describes the potential limitations that impact the inferences that can be drawn from this study along with the likely success of efforts taken to reduce bias.

Study design. Despite the careful selection of appropriate study designs to address the study objectives, there are some limitations. The SCRI design mitigates bias through implicit control for time-fixed confounders. A limitation is that it does not control for time-varying confounders. With the short risk windows for this study, there may be minimal change in confounders, and thus minimal bias would be introduced.

A limitation of the cohort analysis is dis-enrollment from Medicare Parts A, B, and D, which could impact the 365-day baseline period. The feasibility assessment showed that requiring more than 365 days would reduce the sample size because individuals lose Parts A, B, or D coverages. Further, individuals who receive RZV close to age 65, the age at which individuals qualify for Medicare, may not have a full year of enrollment prior to the vaccination date. Consultation with clinical experts confirmed that the 365-day baseline would be adequate to exclude prevalent cases of the HOIs. According to the sample size estimates, the large sample size in the CMS Medicare population should be sufficient, even if the sample is reduced due to less than 365 days of enrollment in Parts A, B, and D prior to the vaccination or preventive care visit date.

Data sources: limitations of the CCW Medicare data.

Services covered by Medicare Advantage (Part C) plans are not included in the CCW Medicare data. Older adults who opt to purchase supplemental insurance are covered under the Medicare Advantage plans, or Part C. All medical encounters and services are paid for by the supplemental insurance, and thus data on these individuals are missing.

Data on clinical metrics, such as laboratory values and illness severity, that could have been used for case identification are not available in the claims data.

Analytic methods. The analytic models selected for the analyses have minimal assumptions, and most of which can be verified through analytic tests and graphical display of the data. However, they could still have some unverifiable assumptions.

Methods to Control for Confounding and Bias. A primary source of confounding in this study are healthy user bias, which refers to the fact that individuals who seek preventive care service may also participate in other healthy behaviors, thus are less likely to experience an outcome. In the cohort analyses, our proposed use of a concurrent preventive care visit as the comparison group will mitigate the effects of healthy user bias on the risk estimate as both RZV vaccinated and unvaccinated will be users of preventive care services.

While other measurable confounding variables that differ between the two groups will be adjusted for in multivariable regression models and possible by using propensity score methods, the risk estimates could still be biased by confounders that were not measured (unmeasured confounders) or not properly measured (residual confounding). A bias analysis is planned to identify how strong an unmeasured confounder must be to explain away the observed effect estimate.

The Dose 2 analysis is conditioned on the subset of individuals who self-select to receive 2 doses within the study period. This may introduce selection bias if there are characteristic differences in measured and unmeasured factors that influence why some individuals receive two doses whereas some only receive one dose. This can underestimate the risk relative to the unvaccinated.

Generalizability. Medicare is the most comprehensive data on older adults, and so the findings will generalize to US adults aged 65 and older. We do not expect appreciable differences between those in the study and those age 65 and older who are not enrolled in Medicare Parts A, B, and D that would affect the HOI risk estimate post-vaccination with RZV.

Sources of random error. The goal is to mitigate bias due to random error. However, it is possible that random sources of error will occur since this is an observational study using secondary claims data. All attempts have been made to ensure appropriate study designs, well-thought out case identification algorithms, appropriate confounder adjustment methods, and planned sensitivity analyses are implemented in the conduct of the study.

Temporal variation. There may be temporal variation due to availability of the vaccine. To address variability in the timing of the vaccine and the preventive care visit, the calendar month-year will be a covariate in the analytic models.

Case ascertainment. It will not be possible to conduct a chart review to validate HOIs. Case-finding algorithms using administrative data are rarely sensitive and specific. The algorithms used in this study are found to have high positive predictive value in published case validation studies and we consulted with experts.

